The sample dimension was calculated using $\alpha = 0.05$ and the power of 80%. For the standard deviation (SD), the value of 0.8 mm obtained in a previous paper (Jepsen et al. 2013). Thus, study was powered to detect a minimum clinically significant difference in root coverage of 0.8 mm between the test and control treatments for root coverage after 6 months. On the basis of these data, the minimum needed number of

patients to be enrolled in this study resulted 28 for the test group (CAF) and 28 for the control group (CAF+ES).

Randomization, allocation concealment, and blinding

The randomization process was performed by an external person who did not participate in the study. Patients were assigned to one of the two treatment groups with the use of computer-generated randomization sequence. Allocation concealment was obtained using sealed coded opaque envelope containing the treatment to the specific subject. The sealed envelope containing the treatment assignment was opened immediately after the surgical procedure by the investigator responsible for the electrical stimulation protocol. The surgeon, patients and investigators who performed clinical measurements were blinded to procedures.

Surgical procedure

All surgical procedures were performed by a single operator ([name]). With a blade 15c (Surgi Blade® - Miami, FL - USA) two horizontal incisions were made at the bases of the mesial and distal papillae of the tooth, towards the adjacent teeth, taking care not to touch the adjacent teeth. From the end of the incisions, two divergent relaxing incisions were performed vertically in the apical direction that surpassed the mucogingival line so that the flap had mobility for coronary traction. A sulcular incision was performed in order to unite the releasing incisions and a split-full-split thickness flap was raised beyond the mucogingival junction (MGJ) (de Sanctis & Zucchelli 2007). After the root planing procedures were performed, the epithelial layer was removed from the incised papillae exposing the connective tissue. Before the flap was positioned coronally, the region was washed copiously with physiological solution to remove the clot allowing intimate contact of the flap with the recipient bed. Sling sutures (5.0 Vicryl™; Ethicon Inc, São José dos Campos, Brazil) were placed to stabilize the flap 2 mm coronal to CEJ, followed by interrupted sutures to close the releasing incisions.

Electric Stimulation Protocol

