The patients allocated in the CAF+ES group received the protocol for electrical stimulation. A unit consisting of a signal generator (Keysight Technologies., Inc., Santa Rosa-CA, USA), a power supply and circuit board, was assembled. Conductive electrodes for electrical current application were positioned on each side of the flap, at a

mean distance of 3 mm from the relaxing incisions and an alternating current with intensity of 100 μ A at 9 kHz, was distributed in order to traverse the operated region. Patients received the stimulus applications for 120 seconds, once a day for 5 consecutive days. The electrical current was optimized through an oscilloscope (Keysight Technologies., Inc., Santa Rosa-CA, USA). All applications were performed by a single researcher involved in the study ([name]). Patients randomized to the CAF group received the simulation of the electrical stimulation process.

Clinical Assessments

Clinical parameters were evaluated at baseline, 3 and 6 months postoperatively as follows: 1) full-mouth visible plaque index (FMPI) (Ainamo & Bay 1975), and presence or absence of visible plaque accumulation at the site included in the study (plaque index [PI]); 2) full-mouth sulcus bleeding index (FMBI) (Muhlemann & Son 1971), and presence or absence of bleeding on probing (BOP) at the site included in the study; 3) PD: measured in millimeters with a periodontal probe (XP23/UNC-15, Hu-Friedy, Chicago, IL); 4) relative GR (RGR): distance from the gingival margin to the incisal border of the tooth; 5) RCAL: measured as PD+RGR; 6) GR: measured at the mid-buccal aspect of the tooth (both RGR and GR quantified using a caliper with a precision of 0.01mm and a pair of dividers); 7) keratinized tissue width (KTW); and 8) keratinized tissue thickness (KTT): measured at the midpoint location between the gingival margin and mucogingival junction as previously described (Fernandes-Dias et al., 2015). A masked and calibrated investigator ([name]) carried out all clinical evaluations. The examiner calibration was performed for PD and RGR using Kappa statistic and intra-class correlation ($k = 0.88$ and $ICC = 0.81$, respectively).

Esthetic evaluation

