To assess the final aesthetic outcome, two analyses were performed, one professional e one patient-centered. The professional evaluation was assessed using the Root Coverage Esthetic Score (RES) (Cairo et al. 2009). For this, two examiners performed the evaluations ([name] and [name]) 6 months after surgeries. The examiners presented previous experience in cosmetic dentistry, were blinded for the treatments and were previously calibrated (intra and inter-examiners $K>0.8$). Esthetic outcomes were also evaluated from the patient's point of view, using a VAS scale pre- and 6 post-operative.

Patient-centered outcomes

At the end of the first postoperative week, the patients completed a questionnaire about the occurrence of discomfort and postoperative pain. The pain was rated by the patient on a VAS scale of 0 to 10 (0 = no sensitivity and 10 = extreme pain). In addition, the patients were asked to report the number of analgesic pills they consumed that week. Dentin hypersensitivity was assessed by 5 s air blast from a triple syringe, applied to the exposed buccal cervical area. A visual analogue scale (VAS) scale (0 = no pain, 10 = extreme pain) was used to record DH related to stimulus. DH was recorded at baseline, 3 and 6 months postoperatively.

Sampling and immunological evaluation

The samples were collected as previously described (Santamaria et al., 2013). Briefly, gingival crevicular fluid (GCF) was collected from the vestibular region of the site that received the CAF. Sampling was performed by introducing filter paper strips (Periopaper; Proflow Inc., Amityville, NY, USA) into sulci until mild resistance was felt, removed after 20 s, and collected fluid volume immediately determined by calibrated instrument (Periotron 8000; Ora Flow Inc., Plain View, NY, USA). The strips were placed in sterile tubes containing 300 ml of phosphate buffered saline (PBS) with 0.05% Tween-2. Strips contaminated with visible blood were discarded. All GCF samples were stored immediately at -80° C. Samples were collected at baseline (before surgery), and 7, 14, 30, 60 and 90 days after surgery.

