Levels of Cito / chemokines were determined by a multiplex immunoassay. Aliquots of each GCF sample were tested using a commercial human kit (Millipore Corporation, Billerica, MA, USA), in order to evaluate levels of the following inflammatory markers: interleukin (IL)-1 β , IL-6, IL-10, tumoral necrosis factor α (TNF α), macrophage inflammatory protein-1 α (MIP-1 α), and chemotactic protein for monocytes-1 α (MCP-1 α). In addition, matrix metalloproteinases (MMP)-2, MMP-9, tissue inhibitor of metalloproteinases (TIMP)-1, TIMP-2 and VEGF were also evaluated. Sample concentrations (antigens in gingival crevicular fluid samples) were estimated from the standard curve using standard kit proteins following manufacturer's instructions and expressed as pg / mL.

STATISTICAL ANALYSIS PLAN

Descriptive statistics were performed using mean \pm standard deviation (SD), and normality was tested using Shapiro-Wilk tests. The PD, RGR, CAL, KTT, KTW, and DH values and also inflammatory markers / growth factors were examined by two-way repeated measures ANOVA to evaluate the differences within and between groups, followed by a Tukey test for multiple comparisons when the Shapiro-Wilk p value was ≥ 0.05 . Data presenting Shapiro-Wilk p values < 0.05 were analyzed using Mann-Whitney tests (for intergroup comparisons) and a Friedman test (for intragroup comparisons). Postoperative discomfort, patient's esthetics measured through VAS and intergroup RES comparisons were analyzed by T-tests. The frequency of complete root coverage (CRC) was compared using χ^2 tests. For all tests a significance level of 0.05 was adopted.

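### The SAP gives one Tukey test to both the within-arm and the between-arm comparisons and names neither the family nor the error term; no single Tukey error term fits both

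*Combined protocol and SAP*

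**What the plan says.** The Statistical Analysis Plan section sends PD, RGR, CAL, KTT, KTW, DH and the inflammatory markers and growth factors through a two-way repeated measures ANOVA "to evaluate the differences within and between groups, followed by a Tukey test for multiple comparisons". This applies when the Shapiro-Wilk p-value is at least 0.05. The section names no set of pairs, no error term and no deciding visit.

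The size of the layout comes from two other sections. Under Clinical Assessments, "Clinical parameters were evaluated at baseline, 3 and 6 months postoperatively". Under Sampling and immunological evaluation, "Samples were collected at baseline (before surgery), and 7, 14, 30, 60 and 90 days after surgery". With two arms that makes 6 cells for clinical variables and 12 for markers.

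The Sample size section powers the trial on one arm comparison, a "minimum clinically significant difference in root coverage of 0.8 mm between the test and control treatments" "for root coverage after 6 months", with 28 patients per arm.

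**The concern.** The sentence asks one procedure to answer two different questions. The randomised question is whether the arms differ at a given visit after surgery. The other is whether an arm changes from visit to visit. The first compares different patients and the second compares patients with themselves, so their standard errors differ. Tukey's range test uses one.

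The sentence also leaves the family open. Depending on how it is read, the arm comparison is held to a threshold far below 0.05, or gets no correction across visits, or becomes an average that includes the visit before surgery. These can give different answers from the same data, and the plan does not settle which applies.

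**Working it through.** **Inputs.** From Sample size: alpha 0.05, power 80%, SD 0.8 mm, difference 0.8 mm, 28 per arm. From Study Population: 60 patients (30 per arm assumed). Visit counts are as above. Assumed: two-sided tests, equal variances, and one common correlation ρ between visits. The documents give no value for ρ, so a range is shown.

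**The plan's own figure.** n per arm = 2(1.96 + 0.84)² × (0.8/0.8)² = 15.7, so 16, or 17 with the t distribution. The stated 28 does not follow from the stated inputs; a difference of 0.6 mm would give it (15.7 × (0.8/0.6)² = 27.9). That is a separate matter. Below I take 28 as given.

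**1. Two variances.**
- Same-visit arm difference: 2σ²/n = 2 × 0.64/28 = 0.0457, SE 0.214 mm.
- Visit-to-visit difference within an arm: 2σ²(1 − ρ)/n. At ρ = 0.5 this is 0.0229, SE 0.151 mm.

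The two SEs differ by the factor √(1 − ρ) and agree only at ρ = 0.

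**2. Tukey over all cells, between-patient error.** The critical |t| is the studentized range quantile divided by √2, with 54 df. The noncentrality for a 1-SD difference is 0.8/0.214 = 3.74.

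| | Clinical | Markers |
|---|---|---|
| Cells | 2 × 3 = 6 | 2 × 6 = 12 |
| Pairs | 15 | 66 |
| Same-visit arm pairs after surgery | 2 | 5 |
| Critical \|t\| | 4.18/√2 = 2.95 | 4.83/√2 = 3.42 |
| Alpha per contrast | 0.0046 | 0.0012 |
| Power, Tukey | 78.0% | 62.8% |
| Power, Bonferroni over post-surgery visits | 92.1% (2 visits) | 85.3% (5 visits) |
| Power, one contrast at 0.05 | 95.7% | 95.7% |

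For a 0.6 mm difference the clinical figures are 44.9% with Tukey and 78.7% for one contrast. At 30 per arm and 0.8 mm, Tukey over 15 pairs gives 82%. The 1-SD effect is planned only for root coverage, so the marker column is illustrative.

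**3. Tukey between two arms within each visit.** With two means, the quantile over √2 is 2.005, which is the ordinary t critical value. Nothing is corrected across visits. If there is no effect, the chance of at least one false arm difference is about 8–10% over 2 post-surgery visits and 15–23% over 5 (ρ from 0.7 down to 0). If contrasts are read only after a significant arm or interaction F, simulation gives about 5% and 6–7%. A single 6-month contrast fixed in advance stays at 5%.

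**4. Tukey on the arm main effect.** This is the ANOVA F test with the between-patient error, and it is valid. It averages over all visits, including the one before surgery, so a constant post-surgery difference shrinks to 2/3 (0.53 of 0.8 mm) for clinical variables and 5/6 for markers.

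**5. If the within-patient residual were the error term.** The SE of the arm difference would be too small by √(1 − ρ). With 3 visits and the ordinary critical value, the false-positive rate at one visit would be about 16% at ρ = 0.5 and 28% at ρ = 0.7. With the six-cell critical value it would be about 4% and 11%. Read only after a significant F, the 16% and 28% fall to about 5–7%.

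**The case against.** The strongest reply is that an unspecified procedure is not a wrong one. A reader might infer that Tukey is the wrong method on any reading, that the false-positive rate is inflated, or that a software default decides the matter. The documents support none of these. They name no family, error term or software. The main-effect reading is valid. Tukey can also suit visit comparisons within an arm, given sphericity, and the same sentence covers those. The high false-positive rates in step 5 need an error term that the plan never mentions and a correlation that has to be assumed, and most of the excess goes if Tukey is read only after a significant F. The over-correction in step 2 costs power and does not inflate error.

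Three further points stand. The trial is powered for one 6-month comparison, and one pre-named contrast needs no correction across visits. The clinical power under the strictest reading (78%, or 82% at 30 per arm) is close to the planned 80%. Root coverage itself is not on the ANOVA list; RGR is the nearest listed variable, and Tukey does not govern complete root coverage, the esthetic scores or non-normal outcomes.

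These points narrow the concern but do not remove it. The SAP section never names 6 months as deciding. Power near 80% under the strictest reading still gives up what the sample would otherwise provide (96%). Conditioning on the F test is itself not stated, and it does not protect when some visits differ and others do not.

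**Conclusion.** The point holds as under-specification with a practical cost. One Tukey error variance cannot fit both comparisons unless ρ is zero, which is unlikely for repeated measurements at one site. The all-cell reading tests the arm comparison at 0.0046 or 0.0012 where 0.05, or 0.025 over two visits, would do. It takes clinical power from 96% to 78% at the plan's SD and difference. The per-visit reading leaves about 8–10% over two post-surgery visits, or about 5% after a significant F, and this counts only if any visit may be claimed. The main-effect reading dilutes the treatment effect with baseline.

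The step 2 figures rest on 28 per arm and an SD of 0.8 mm, which the plan gives for root coverage and which I have carried over to the ANOVA variables. The error rates in steps 3 and 5 rest on equal correlations between visits and, except for the 5% of a single pre-named contrast, on the assumed value of ρ. It should not be said that the plan chose the within-patient residual for the arm comparison.

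**What to change.** Replace the Tukey clause for between-arm comparisons with wording to this effect:

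- Arms are compared only at the same post-surgery visit, by contrasts from the repeated-measures model, using the standard error for between-patient differences.
- For clinical outcomes the 6-month contrast is the named deciding one and is tested alone at 0.05. Alternatively, p-values are Holm-adjusted over the 2 post-surgery visits.
- For markers, p-values are Holm-adjusted over the 5 post-surgery visits within each marker.
- Visit comparisons within an arm, if wanted, form a separate secondary family with their own within-patient error term.
- Pairs that cross both arm and visit are not tested.

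The cost is slightly more SAP text and analysis, and within-arm p-values become secondary. No design or data collection changes. Holm is one reasonable choice; Bonferroni would also do. This does not deal with multiplicity across the 11 markers, which needs its own statement.

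### A Shapiro-Wilk test with no stated unit picks the analysis of the gated outcomes; neither branch adjusts for baseline, and no single between-arm contrast is fixed in advance

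*Combined protocol and SAP*

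**What the plan says.** The Statistical Analysis Plan states: "The PD, RGR, CAL, KTT, KTW, and DH values and also inflammatory markers / growth factors were examined by two-way repeated measures ANOVA", with the aim "to evaluate the differences within and between groups", "followed by a Tukey test for multiple comparisons when the Shapiro-Wilk p value was ≥ 0.05". The alternative is: "Data presenting Shapiro-Wilk p values < 0.05 were analyzed using Mann-Whitney tests (for intergroup comparisons) and a Friedman test (for intragroup comparisons"). Discomfort, patient-rated esthetics and RES (t-tests) and complete root coverage (chi-square) are outside this gate.

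Baseline exists for every gated outcome. Under Clinical Assessments, "Clinical parameters were evaluated at baseline, 3 and 6 months postoperatively". DH follows the same schedule (Patient-centered outcomes). GCF is sampled before surgery and at five later times up to day 90 (Sampling and immunological evaluation). RGR is the "distance from the gingival margin to the incisal border of the tooth", and RCAL is PD plus RGR; the analysis section lists the attachment level as CAL.

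Under Sample size, the "study was powered to detect a minimum clinically significant difference in root coverage of 0.8 mm between the test and control treatments" at 6 months. On variability: "For the standard deviation (SD), the value of 0.8 mm obtained in a previous paper". The stated result is 28 per group.

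**The concern.** Four things are left open.

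- **Unit of the gate.** Shapiro-Wilk could be applied to residuals, changes, pooled values, or each arm at each visit. No rule covers disagreement among these.
- **ANOVA term.** The treatment test could be the group main effect, the group-by-time interaction or a Tukey contrast. If baseline is a level of the time factor, the interaction compares change between arms. The main effect averages in a baseline visit that cannot contain a treatment effect.
- **Rank branch.** Mann-Whitney is named between groups, but not the visit, nor whether values or changes are compared.
- **Baseline.** It is a covariate in neither branch.

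At stake are precision, exposure to chance baseline imbalance, and a treatment test unknown until the data are seen. RGR matters most. Crown height is part of every RGR and RCAL value, and it cancels only if change is compared or baseline is adjusted for.

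**Working it through.** **Inputs.** From the plan: difference 0.8 mm, SD 0.8 mm, alpha 0.05, 28 per group; 3 clinical visits and 6 GCF samples. Assumed: two-sided tests; visit correlation r = 0.3 / 0.5 / 0.7; for RGR, crown SD 0.5 to 1.2 mm, baseline recession SD 0.6 mm, and correlation of coverage with baseline recession ρ = 0 or 0.5.

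**The plan's own figure.** n = 2(1.96 + 0.84)² × (0.8/0.8)² = 15.7, so 16 per arm (17 with the t distribution), not 28. A 0.6 mm difference would give 28. That is a separate matter; 28 per arm is used below. Power there at 1.0 SD is Φ(1/√(2/28) − 1.96) = Φ(1.78) = 96.3%.

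**Precision.** The variance of ANCOVA relative to follow-up values is 1 − r² = 91 / 75 / 51%. Relative to changes it is (1 + r)/2 = 65 / 75 / 85%. These ratios hold at any effect size. The chance of a baseline difference above 0.25 SD is 2(1 − Φ(0.25/√(2/28))) = 35%.

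**Power, 28 per arm, normal data (10,000 simulated trials per row; ANOVA rows use 3 visits, equal correlation and an equal effect at 3 and 6 months):**

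| Test (r = 0.3 / 0.5 / 0.7) | 1.0 SD (plan's ratio) | 0.75 SD (assumed) |
|---|---|---|
| Mann-Whitney, follow-up | 95 / 94 / 94% | 76 / 76 / 76% |
| ANOVA group main effect | 92 / 85 / 78% | 71 / 61 / 53% |
| ANOVA group-by-time | 91 / 97 / 99.9% | 67 / 83 / 97% |
| ANCOVA | 97 / 99 / 99.9% | 81 / 88 / 97% |

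ANCOVA's gain over Mann-Whitney on follow-up is about 2 to 6 points at 1.0 SD and 5 to 21 at 0.75 SD. Over group-by-time at 1.0 SD it is about 0 to 6.

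**RGR.** Take the 6-month value as baseline minus coverage, with coverage SD 0.8 mm and arm difference 0.8 mm. The 6-month variance is crown² + 0.6² + 0.8² − 2ρ(0.6)(0.8).

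- Crown 1.2, ρ = 0: 1.44 + 0.36 + 0.64 = 2.44; SD 1.56; effect 0.51 SD; Φ(0.512/0.267 − 1.96) = 48%.
- Crown 0.5, ρ = 0.5: 0.25 + 0.36 + 0.64 − 0.48 = 0.77; SD 0.88; effect 0.91 SD; Φ(0.912/0.267 − 1.96) = 93%.

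These are normal approximations. Simulated Mann-Whitney on 6-month values runs from about 44% to 90%. Change removes crown height, leaving 0.8/0.8 = 1.0 SD: 95% to 96% by t-test, about 97% by group-by-time. ANCOVA gives 95% to 98%.

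**Gate, truly normal data, 30 per arm.** If the unit is every arm-visit cell and any failure switches the outcome, the switching rate with independent cells is 1 − 0.95⁶ = 26.5% for clinical outcomes and 1 − 0.95¹² = 46.0% for a marker (simulated 24% to 28% and 40% to 47%). Change tested in each arm gives 9% to 11%; pooled ANOVA residuals give 3% to 5%.

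**Error rate.** With one test fixed per branch (group-by-time, or Mann-Whitney at 6 months), the gated procedure kept 4.6% to 5.4%. If either the main effect or the interaction may count, the rate is 1 − 0.95² = 9.75% (simulated 9.5% to 10.2%). If Mann-Whitney at 3 or 6 months may count, it is 8.1% to 9.8%.

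**The case against.** The strongest reply is that the planned tests are sound and the covariate is a matter of efficiency. Much of that stands. Mann-Whitney between randomised arms is valid, and group-by-time is a valid comparison of change. At the plan's ratio, Mann-Whitney on follow-up and group-by-time both have at least 91% power, so there is little left to gain. For RGR, change or group-by-time is about as powerful as ANCOVA. Switching itself costs little on normal follow-up data: t-test 79% against Mann-Whitney 76% at 0.75 SD.

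Three stronger readings are tempting, and the documents do not support them.

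- A reader might infer that the rank branch contains no between-arm comparison of change. The plan does not say whether values or changes enter Mann-Whitney, so only silence can be asserted.
- A reader might infer that the gate inflates type I error. The simulations show it does not once the test in each branch is fixed. The rate of about 10% arises only if either ANOVA term may be read as the result, which the plan does not announce but does not exclude.
- A reader might take the ANOVA main effect as the treatment test and quote RGR power of 28% to 76%. The plan never adopts that reading, and the crown SD behind it is assumed.

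The group-by-time figure for RGR is also conditional. It uses an uncorrected F. If 3- and 6-month coverage correlate at an assumed 0.8 to 0.95, the false-positive rate of that F is about 6% to 8%. The t-test on change does not depend on this.

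What the reply does not answer is that the plan fixes neither the term, the visit nor the scale, and leaves a collected baseline unused as a covariate.

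**Conclusion.** The point holds as a matter of precision and prespecification. It does not show bias or an invalid test. A missing unit for Shapiro-Wilk would be only a missing detail by itself. It matters here because the gate decides between branches that leave the treatment contrast open.

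At the plan's 1.0 SD the loss is small for most outcomes. That ratio concerns root coverage, which is not named among the gated outcomes; RGR is the nearest. The loss can be large for RGR, and RCAL shares the exposure, if 6-month values are what is compared. The variance ratios rest on assumed correlations, and the RGR range on an assumed crown SD and on reading the plan's 0.8 mm as the SD of coverage. The change is worth making, but the trial does not fail without it.

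**What to change.** Drop the normality gate. For each gated outcome, prespecify one between-arm analysis with baseline as covariate: ANCOVA, or a mixed model with group-by-visit terms. Name one contrast: 6 months for clinical outcomes; for markers, either a contrast chosen in advance or the joint group-by-visit test. Give an estimate and 95% CI wherever a single contrast is used. For outcomes expected to be skewed or bounded (the markers, and clinical outcomes such as DH), fix log-scale or rank ANCOVA in advance. Keep Friedman and other within-arm tests as description. If the gate is kept, the minimum is to state its unit, the ANOVA term, and the visit and scale for Mann-Whitney.

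The cost is wording and slightly more modelling, with no new data. Log-scale results are read as ratios. Two choices need care.

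- **Scale.** For lognormal data with log-SD 1.0 at 0.75 SD, unlogged ANCOVA has only 61 / 66 / 79% power, against 75% to 77% for Mann-Whitney across log-SDs of 0.5 to 1.0. Log-scale ANCOVA has about 81 / 88 / 97% and rank ANCOVA about 80 / 86 / 95%.
- **Marker contrast.** For an effect only at days 7 and 14 (0.75 SD), the mean over the five postoperative samples has 45% to 56% power, against 86% to 99.9% for group-by-time. An averaged contrast could therefore hide an early effect.

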**Electrical stimulation effect on coronally advanced flap
for the treatment of single gingival recession:
randomized controlled clinical trial**

UNESP – São Paulo State University. Dept. of Periodontology, College of
Dentistry

ClinicalTrial.org- NCT02987231

São José dos Campos, São Paulo - Brazil

August 15th, 2016

STUDY PROTOCOL

This investigation was a parallel, double-blind, randomized clinical trial. The study protocol (ClinicalTrial.org- NCT02987231) was approved by the Institutional Review Board at College of Dentistry – São José dos Campos, State University of São Paulo (1.679.369-UNESP). Each subject provided informed consent after a thorough explanation of the nature, risks, and benefits of the clinical investigation.

Study Population

Sixty patients from the Periodontology Clinic, UNESP—State University of São Paulo (São José dos Campos, Brazil), presenting 60 maxillary buccal gingival recessions in their canines and premolars were included in the study. The subjects were selected in the period between October 2016 and December 2017, according to the following eligibility criteria: 1) ≥ 18 years 2) periodontally and systemically healthy 3) FMPS and FMBS $\leq 20\%$ 4) single Cairo's class RT1 gingival recession (Cairo et al., 2011) in the maxillary canines or premolars ($\geq 3\text{mm}$ depth) at the buccal 5) presence of identifiable CEJ 6) no previous periodontal surgery at the affected teeth. Study exclusion criteria: 1) systemic problems that would contraindicate the surgical procedure; 2) patients taking medications known to interfere with the wound healing process or that contraindicate the surgical procedure; 3) smokers and pregnant women; 4) patients who underwent periodontal surgery in the area of interest; 5) patients undergoing orthodontic treatment.

Before surgery, Patients received oral hygiene instructions (roll technique) with a soft-bristled toothbrush to correct wrong habits related to the etiology of the recession. All participants received a session of prophylaxis and scaling. The surgical treatment was performed only when patients achieved adequate plaque control (full-mouth plaque score $\leq 15\%$)

Sample size

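### The esthetic VAS is recorded before and after surgery, but the SAP names only t-tests for it, without stating which score is analysed or adjusting for the pre-operative score

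*Combined protocol and SAP*

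**What the plan says.** The protocol section on esthetic evaluation has patients score their own esthetics "using a VAS scale pre- and 6 post-operative". The unit after the 6 is not printed. Six months is the natural reading, because the professional score (RES) and the last clinical visit are at 6 months.

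The Statistical Analysis Plan deals with this outcome in one sentence, which also covers postoperative discomfort: "esthetics measured through VAS and intergroup RES comparisons were analyzed by T-tests". It does not name the score that enters the test.

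Probing depth, recession, attachment, keratinized tissue, dentin hypersensitivity and the GCF markers are treated differently: they "were examined by two-way repeated measures ANOVA to evaluate the differences within and between groups". Dentin hypersensitivity is also a patient VAS with a baseline, and it is on that list. The esthetic VAS is not. No outcome in the plan has a baseline covariate.

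**The concern.** The SAP sentence groups three outcomes that differ in one respect. No pre-operative value is described for first-week discomfort or for RES, so a two-sample t-test is a natural choice for both. The esthetic VAS does have one, and the sentence makes no stated use of it.

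Two things follow. The analysis is not pinned down: a t-test on follow-up scores, a t-test on change and a paired test within each arm all fit the wording, and they answer different questions or have different precision. And no reading makes the best use of a baseline that has already been collected. At stake is the precision of the between-arm estimate for one of the two assessments of the final esthetic result, and the possibility that the choice among three analyses is made after the data are seen.

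**Working it through.** **The plan's own figures.** The documents give no SD, target difference, correlation or power for the esthetic VAS, so there is nothing on this outcome to reproduce. The only design figure is 28 per group, for root coverage, from an SD described as "the value of 0.8 mm obtained in a previous paper" and a "minimum clinically significant difference in root coverage of 0.8 mm". With two-sided 0.05 and 80% power those inputs give n = 2 × (1.960 + 0.842)² × (0.8/0.8)² = 15.7, so 16 per group (17 with the t distribution), not 28. That is a separate matter and has no bearing on this point.

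**Inputs**
- Patients: "Sixty patients from the Periodontology Clinic". The split is not stated; 30 per arm is assumed.
- Alpha: "For all tests a significance level of 0.05 was adopted". Sidedness is not stated; two-sided is assumed.
- Standardised difference d = 0.6: assumed.
- Equal SD before and after surgery: assumed.
- Correlation r between pre-operative and 6-month VAS: unknown; varied from 0 to 0.6.

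**Precision of each between-arm analysis.** Write the variance of the between-arm difference as k × (2/n) × SD².
- Follow-up score only: k = 1.
- Change score: k = 2(1 − r). This exceeds 1 whenever r < 0.5, so a change-score test is then less precise than ignoring the baseline.
- ANCOVA: k = 1 − r², multiplied by a small-sample factor (2n − 3)/(2n − 4) = 57/56 = 1.018 for estimating the slope.
- Change minus ANCOVA, before that factor: 2(1 − r) − (1 − r²) = (1 − r)², which is never negative.
- Paired pre/post test within each arm: no between-arm difference is estimated, so k does not apply.

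**Power.** In SD units the standard error is √(2/30) × √k = 0.2582√k, and the noncentrality is 0.6/(0.2582√k). The critical t is 2.002 on 58 df for the t-tests and 2.002 on 57 df for ANCOVA. Follow-up only: noncentrality 0.6/0.2582 = 2.324, power 62.8%.

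| r | k, change | k, ANCOVA (with 57/56) | Noncentrality: change / ANCOVA | Power, change | Power, ANCOVA | ANCOVA vs follow-up only |
|---|---|---|---|---|---|---|
| 0 | 2.0 | 1.018 | 1.643 / 2.303 | 36.6% | 62.0% | about −1 point |
| 0.2 | 1.6 | 0.977 | 1.837 / 2.351 | 43.9% | 63.7% | about +1 |
| 0.3 | 1.4 | 0.926 | 1.964 / 2.415 | 48.9% | 66.0% | about +3 |
| 0.5 | 1.0 | 0.763 | 2.324 / 2.660 | 62.8% | 74.4% | about +12 |
| 0.6 | 0.8 | 0.651 | 2.598 / 2.879 | 72.4% | 80.8% | +18 |

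Without the small-sample cost, the ANCOVA figures at r = 0.3, 0.5 and 0.6 would be 66.8%, 75.1% and 81.5%.

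**The case against.** **The plan may use the baseline.** A reader might infer that the named t-test ignores the pre-operative score. The documents do not say so. In the SAP sentence the word for a between-group comparison attaches to RES, and a t-test on change or a paired test would both use the baseline. What the text supports is that the analysed score is unspecified and that no baseline adjustment is planned. This changes the diagnosis but not the remedy, since each of the three readings falls short in its own way.

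**A t-test on follow-up scores is valid.** A reader might infer bias from a chance imbalance in pre-operative scores. Allocation is computer-generated and concealed, so this test is unbiased over randomisations and keeps its type I error. Given an imbalance that has occurred, only a fraction r of it is expected to carry into the follow-up difference when the SDs are equal: about 30% at r = 0.3. This objection stands, and the point is one of efficiency.

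**The gain may be small.** Surgery takes place between the two ratings, and nothing in the documents shows that r reaches 0.5. At r of 0.1 or less the gain is nil or slightly negative; at 0.3 it is about 3 points. This also stands, which is why the table starts at r = 0.

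**Importance.** The plan ranks no esthetic outcome and powers the trial only on root coverage, so a reader should not take this VAS as a principal patient-centred endpoint. It is one of several unpowered outcomes.

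**Conclusion.** The point holds as a matter of specification and efficiency. The SAP does not say which esthetic VAS score is tested, and it plans no adjustment for a baseline that the protocol collects. ANCOVA is at least as precise as either between-arm t-test, apart from a small-sample cost of under 1 point of power when r is zero.

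On the assumptions listed (30 per arm, two-sided 0.05, d = 0.6, equal SDs, 6 meaning 6 months), power against a follow-up-only t-test changes by between about −1 point (r = 0) and +18 points (r = 0.6). The improvement is modest at r = 0.3 and material from about r = 0.5. None of these inputs except the 0.05 level and the total of 60 comes from the documents, so the range matters more than any single figure. The documents do not support reading this as a biased or invalid analysis.

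**What to change.** Replace the SAP wording for this outcome with one sentence: the 6-month patient esthetic VAS is compared between arms by ANCOVA with the pre-operative VAS as covariate, and the adjusted mean difference is reported with its 95% CI. State the time unit of the post-operative rating in the protocol's esthetic section. If a t-test is kept instead, the SAP should at least say which score it uses and that it compares the arms.

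Leave RES and first-week discomfort on t-tests, since no pre-operative value is described for either.

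The cost is one SAP sentence and one degree of freedom in the analysis. No new data are needed.
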